## FAMILY HISTORY OF CAD

Any first degree relatives (parents, siblings or offspring) who have had any of the following at age less than 55 years in case of male and less than 65 years in case of female-

1. Typical Angina or
2. Myocardial Infarction
3. Sudden cardiac death without obvious cause.

## CORONARY ARTERY DISEASE

Patients with a 70% narrowing in one or more of the following is considered to have significant angiographic coronary artery disease: the left anterior descending, left circumflex, right coronary arteries or their major branches, or a 50% narrowing in the left main coronary artery. Ischemic heart disease and coronary artery disease terms are used interchangeably (Kern M.J. 2013).

The extent and severity of CAD is defined as 1-vessel, 2-vessel, 3-vessel, or left main disease, with a significant stenosis  $\geq 70\%$  diameter reduction. (Neglia, et al., 2015)

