### **Coronary Angiography**

Coronary artery narrowing will be visually estimated and expressed as percent lumen diameter stenosis. Patients with a 70% narrowing in one or more of the following is considered to have significant angiographic coronary artery disease: the left anterior descending, left circumflex, right coronary arteries or their major branches, or a 50% narrowing in the left main coronary artery (Kern 2013).

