### Coronary angiogram:

29. Extent of disease: 0= Normal, 1=SVD, 2=DVD, 3=TVD, 4=LM

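### The extent definition requires at least 70% stenosis for left main disease, while the plan's own CAD definition uses 50%, so an isolated 50–69% left main lesion is CAD-positive but has no extent class

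*Combined protocol and SAP*

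**What the plan says.** Under Procedures during study, Coronary Angiography: "Coronary artery narrowing will be visually estimated and expressed as percent lumen diameter stenosis". The binary rule follows: "Patients with a 70% narrowing in one or more of the following is considered to have significant angiographic coronary artery disease". The list covers the left anterior descending, left circumflex and right coronary arteries and their major branches, "or a 50% narrowing in the left main coronary artery".

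The first paragraph of Operational Definitions, Coronary Artery Disease repeats that rule, left main at 50% included. The second paragraph defines a different variable: "The extent and severity of CAD is defined as 1-vessel, 2-vessel, 3-vessel, or left main disease, with a significant stenosis". The words directly after put that stenosis at ≥70% diameter reduction. Left main is named in the list and given no separate threshold.

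In Appendix C the angiogram result is one item: "29. Extent of disease: 0= Normal, 1=SVD, 2=DVD, 3=TVD, 4=LM". The form header adds only the angiogram date and a CD number. There is no field for percent stenosis and none for significant CAD yes/no. Statistical Methods uses angiographic CAD as the reference for every ROC curve, and the dummy cross-tables classify patients by CAD status. No section says how that status is obtained from the form.

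**The concern.** Two adjacent paragraphs treat the same lesion differently. A patient whose only important lesion is a 50–69% left main narrowing has significant CAD by the first. By the second, that patient is not in 1-vessel, 2-vessel, 3-vessel or left main disease.

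Two things are at stake. The first is the severity scale for Specific Objective 3, which relates score level to severity of CAD: as written, it can leave a CAD-positive patient without a severity class. The second is conditional. If the analyst builds CAD status from item 29, and this patient was entered as 0, the patient joins the CAD-free group. Every score that flagged the patient is then charged with a false positive.

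**Working it through.** **The rules side by side**

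| Angiographic finding | CAD by the stated CAD definition | Extent class by the ≥70% rule | Item 29 if the extent rule is followed |
|---|---|---|---|
| Isolated left main, 50–69% | Yes | None | Only 0 is left |
| Isolated left main, ≥70% | Yes | Left main | 4 |
| Left main 50–69% plus another vessel ≥70% | Yes | By vessel count | 1–3 (still CAD) |
| Left main ≥70% plus another vessel ≥70% | Yes | Left main and vessel disease | One code only (still CAD) |
| Non-left-main lesion below 70% | No | None | 0 (correctly not CAD) |

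Only the first row changes binary CAD status. The last three rows show loss of detail or a poor label, not misclassification, provided the stated thresholds are followed.

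**Size for one such patient coded 0**

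The plan gives no figure to reproduce on this point. Inputs:

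- Sensitivity 74% and specificity 73%: cited in the Literature Review for the Duke score cut-off of −3.7, used here as an example test.
- CAD-free patients: 38 or 23, both assumptions. The 38 has no source in the documents. The 23 comes from 102 × (1 − 0.779) = 22.5, where 77.9% is the local positive predictive value in the Literature Review. That value describes patients with a positive treadmill test, and inclusion here does not require one, so 23 is illustrative only.

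With m CAD-free patients and one CAD patient moved among them:

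- Score flagged the patient: apparent specificity = 0.73m / (m + 1)
- Expected, given a 74% chance of being flagged: (0.73m + 0.26) / (m + 1)

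For m = 38:

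- Flagged: 27.74 / 39 = 71.1%, a loss of 1.9 points.
- Expected: 28.00 / 39 = 71.8%, a loss of 1.2 points.

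For m = 23:

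- Flagged: 16.79 / 24 = 70.0%, a loss of 3.0 points.
- Expected: 17.05 / 24 = 71.0%, a loss of 2.0 points.

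If the score did not flag the patient, apparent specificity rises slightly: 28.74 / 39 = 73.7%, or 17.79 / 24 = 74.1%.

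Expected change in overall accuracy per patient: (0.74 − 0.26) / 102 = 0.47 points lost.

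**Range over frequency and prevalence**

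Assume 1% to 5% of 102 patients (about 1 to 5) are affected and all are coded 0. Expected apparent specificity falls from 73% to between 72.1% and 68.7% at 50% CAD prevalence, and to between 71.5% and 66.3% at 70%. Accuracy falls by about 0.5 to 2.4 points.

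**The case against.** The strongest reply is that the reference standard is not ambiguous. The binary CAD rule is stated twice in the same terms, and the ≥70% sentence defines extent, a separate variable. Sampling Procedures says the angiogram report will be collected, so percent stenosis can be recovered at source. A coder working from the CAD definition would enter left main at 50%. Harm to the accuracy analyses needs three steps: the 70% rule is applied to left main, the patient is entered as 0, and CAD status is derived only from that code.

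Most of this stands. A reader might infer that every ROC curve and cross-table rests on item 29, because it is the only angiographic result on the form. The documents do not say so, and the effect on the reference standard must stay conditional. What the reply does not remove is the conflict between the two paragraphs, or the lack of any instruction that would prevent those three steps.

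It might also be inferred that code 0, labelled Normal, and the single code for left main plus other-vessel disease corrupt CAD status. They do not if the thresholds are followed: a sub-threshold lesion entered as 0 is correctly CAD-free, and left main plus vessel disease is CAD-positive under any of codes 1 to 4.

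Finally, all scores share one reference in the same patients. An error of this kind moves them largely together, so it bears more on absolute accuracy than on the between-score comparison that is the general objective.

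**Conclusion.** The point holds as an internal inconsistency. Followed as written, the plan gives an isolated 50–69% left main lesion a positive CAD status and no extent class. The severity scale for Specific Objective 3 therefore does not match the CAD definition, and Statistical Methods names no analysis for that objective that would settle the matter. The reference standard is misclassified only if CAD status is derived from item 29.

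The likely effect is small: an expected 1.2 points of apparent specificity per affected patient with 38 CAD-free, or 2.0 with 23. This rests on the cited 74% and 73%, on assumed counts, and on the patient being coded 0. How often such lesions occur is not in the documents.

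Dividing one patient by 38 or by 23 suggests 2.6 or 4.3 points. Those are upper bounds: they leave the moved patient out of the denominator, assume specificity near 100%, and assume the score flagged the patient. The documents do not support them as the expected cost. A material distortion of the differences between scores has not been shown either.

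**What to change.** Reconcile the two paragraphs of the Coronary Artery Disease definition so that extent uses the same thresholds as the CAD definition the plan already states twice. This is a matter of consistency, not a judgement on which threshold is clinically better.

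On the form:

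- Relabel code 0 of item 29 as no significant stenosis.
- Add a CAD yes/no field derived by the Coronary Angiography definition.
- Record left main involvement separately from the number of diseased vessels.

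Add one sentence to Statistical Methods naming the yes/no field as the source of CAD status for the ROC curves and cross-tables.

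The cost is one revised definition, that sentence, one relabelled code and a few extra form fields. All the data come from the angiogram report already being collected, so no additional procedure is needed.

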## CORONARY ANGIOGRAM/ CARDIAC CATHETERIZATION

Left heart catheterization or coronary arteriography remains the clinical gold standard for determining the presence of significant coronary artery disease (CAD).

Cardiac catheterization is the insertion and passage of small plastic tubes (catheters) into the heart to obtain x-ray pictures (angiography) of coronary arteries. The cardiac catheterization laboratory performs angiography to obtain images to diagnose coronary artery disease as well as other disease condition (Kern M.J. 2013).

## Stable IHD

Anginal symptoms are defined as stable if there is no substantial change in symptoms over several weeks. Symptoms of stable angina can fluctuate from time to time, depending on myocardial oxygen consumption, emotional stress, or change in ambient temperature. In general, the clinical definition of stable angina pectoris closely correlates with the stability or quiescence of an atherosclerotic plaque and decreased clinical risk.

Chest pain is defined as “typical angina” if it consists of characteristic (1) substernal discomfort, (2) is provoked by stress, and (3) is relieved by rest or nitroglycerin. It is considered “atypical” if it involves two or less of the previously mentioned criteria. (Griffin 2013)

## Appendix A

### Treadmill Scores and their calculation

The DTS will be calculated as  $DTS = \text{exercise time} - (5 \times \text{ST deviation}) - (4 \times \text{exercise angina})$ , with 0 = none, 1 = non-limiting, and 2 = exercise-limiting angina. The METs will be calculated by modified Bruce protocol and be inputted into the DTS equation (Fletcher et al., 1995). Based on the study by Shaw *et al.* (1998), a  $DTS < +5$  is considered abnormal. High risk when  $DTS < -10$  and low risk when  $DTS > +5$ .

The simple Treadmill Score for men will calculated as follows:

$(6 \times \text{maximal heart rate code}) + (5 \times \text{ST-segment depression code}) + (4 \times \text{age code}) + \text{angina pectoris code} + \text{hypercholesterolemia code} + \text{diabetes code} + \text{treadmill angina index code}$ .

The simplified score had a range from 6 to 95, with  $< 40$  designated as low probability, between 40 and 60 was intermediate probability, and  $> 60$  was high probability for CAD.

For male patient

Variable	Choose Response	Sum
Maximal HR	$<100 \text{ bpm} = 30$	
	$100-129 \text{ bpm} = 24$	
	$130-159 \text{ bpm} = 18$	
	$160-189 \text{ bpm} = 12$	
	$190-220 \text{ bpm} = 6$	
Exercise ST depression	$1 - 2 \text{ mm} = 15$	
	$>2 \text{ mm} = 25$	
Age	$>55 \text{ yr} = 20$	
	$40-55 \text{ yr} = 12$	
Angina history	Definite/typical = 5	
	Probable/atypical = 3	

[figure not shown]
	Non-cardiac pain = 1	
Hypercholesterolemia	Yes = 5	
Diabetes	Yes = 5	
Exercise test: induced angina	Occurred = 3	
	Reason for stopping = 5	
	Total score:	

For Female patients

Variable	Choose Response	Sum
Maximal HR	<100 bpm = 20	
	100-129 bpm = 16	
	130-159 bpm = 12	
	160-189 bpm = 8	
	190-220 bpm = 4	
Exercise ST depression	1 – 2 mm = 6	
	>2 mm = 10	
Age	>65yr = 25	
	50-65 yr = 15	
Angina History	Definite/typical = 10	
	Probable/atypical = 6	
	Non-cardiac pain = 2	
Smoking	Yes = 10	
Diabetes	Yes = 10	
Exercise test: Induced angina	Occurred = 9	
	Reason for stopping = 15	
Estrogen status	+ve = -5, -Ve = 5	
	Total =	

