### **Sampling Procedures**

Patient presented with stable chest pain, who have undergone ETT according to Bruce protocol and admitted for CAG, will be selected as case considering inclusion and exclusion criteria. Detailed and thorough clinical assessment will be done and recorded. All available previous medical documents will be checked meticulously. Patients with previous revascularization, left bundle-branch block, paced rhythms or Wolff-Parkinson-White syndrome (WPW) on resting electrocardiogram (ECG), or valvular heart disease, congenital heart disease will be excluded from the study. To avoid falsely increasing the accuracy of the exercise treadmill test, patients with a previous myocardial infarction by history or by diagnostic Q wave will be excluded.

With history, clinical findings and investigations cases other than stable chest pain will be excluded. Informed written consent will be taken from the patient. CAG report will be collected from the Cath lab after the procedure.

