## **Procedures during study**

### **Exercise Treadmill Testing**

Patients will be undergoing treadmill testing using Bruce treadmill protocol. Before treadmill testing, the patients will be given a questionnaire. This questionnaire will estimate the patient's exercise capacity before the test and thus will allow most patients to reach maximal exercise capacity (Myers 1994). Visual ST-segment deviation will be measured at the J junction and will be corrected for pre-exercise ST-segment depression while standing; ST slope will be measured over the following 80 ms and will be classified as up sloping, horizontal, or down sloping. Slope will be coded as 1 horizontal, down sloping, or upsloping ST depression and 0 for normal slope (up sloping  $<2$  mm or ST-segment depression of  $<0.5$  mm). The ST response will be considered which has the most horizontal, downsloping or up sloping ST-segment depression in any lead, except aVR, during exercise or recovery. An abnormal response will be defined as  $\geq 1$  mm of horizontal or downsloping or  $\geq 2$  mm upsloping ST-segment depression (Griffin 2013). The exercise tests will be analyzed, and reported per standard protocol and manual calculation. Decision for cardiac catheterization will be consistent with clinical practice. Analyses will be performed with the investigators blinded to clinical and angiographic results.

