## Statistical Methods

Using angiographic evidence of CAD as the reference, area under the curve (AUC) of receiver operator characteristic (ROC) plots will be determined for the ST response alone and for each treadmill score. The AUC for each treadmill score will be compared with the AUC of the ST response alone and the AUCs of the other treadmill scores. A significant difference is defined as a z-score  $>1.96$ , with  $z\text{-score} = (AUC_1 - AUC_2) / (\text{SE}_1^2 + \text{SE}_2^2)^{1/2}$ . The predictive accuracies of the DTS, the Simple Treadmill Score and Cleveland Clinic Score to stratify patients into high or low likelihood for CAD will be calculated and compared. Test of agreement will be calculated using Kappa statistics. Statistically significant difference between predictive accuracies is defined as a p value  $<0.05$  using the two-tailed Fischer's exact test. Statistical analysis will be performed with the SPSS.

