### Exercise test variables:

18. Duration of exercise: .....min

19. METs .....

20. Maximum Heart Rate: .....bpm

21. Peak Systolic BP: .....mmHg

22. Maximum ST segment depression: .....mm

23. Exercise induced angina: 0= No angina 1= Non-test limiting

2= Test limiting angina

24. Abnormal heart rate recovery: 0= No 1= Yes

25. Frequent VE during recovery: 0= No 1= Yes

26. Duke Treadmill Score: ..... 0= Low risk

1= High risk

27. Simple Treadmill Score: ..... 0=Low probability

1=High probability

28. Cleveland Clinic Score: ..... 0=Low probability

1= High probability

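### The Duke Treadmill Score is defined from exercise time, but the plan then says METs go into the same equation, which has no MET term

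*Combined protocol and SAP*

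**What the plan says.** Appendix A (Treadmill Scores and their calculation) gives DTS three terms: exercise time, ST deviation with weight 5, and exercise angina with weight 4, the last coded "with 0 = none, 1 = non-limiting, and 2 = exercise-limiting angina". The next sentence reads "The METs will be calculated by modified Bruce protocol and be inputted into the DTS equation". The cut-offs follow once only: below +5 is abnormal, above +5 is low risk and below -10 is high risk.

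The sections on conduct of the test name a different protocol. Exercise Treadmill Testing says "Patients will be undergoing treadmill testing using Bruce treadmill protocol", and Sampling Procedures describes patients "who have undergone ETT according to Bruce protocol".

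The data form in Appendix C has "18. Duration of exercise: .....min" and, as item 19, a separate field for METs. The score itself is entered as "26. Duke Treadmill Score: ..... 0= Low risk", with 1 for high risk. The form does not say which of the two exercise fields feeds the score.

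Statistical Methods uses the resulting class. The accuracies of the three scores "to stratify patients into high or low likelihood for CAD will be calculated and compared", and "Test of agreement will be calculated using Kappa statistics". The dummy tables cross the DTS class with angiographic CAD.

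**The concern.** The definition and the instruction that follows it cannot both be carried out as written. Either METs replace exercise time, or they are a step towards an equivalent exercise time that the plan does not print.

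Under the first reading, DTS is computed from a different quantity and compared with cut-offs that are not adjusted for it. A patient can then change class for a reason unrelated to the diagnostic value of the score. Under the second reading, the conversion is missing and two people scoring the same form could reach different results.

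The consequence falls on planned results. DTS is one of the three scores compared, its low/high class enters the accuracy comparison and kappa, and its predictive accuracy (0.71 against 0.55) is the quantity on which the study was sized. The plan says tests are reported with manual calculation, so the written definition is the main control on how the score is formed. A scoring artefact could be reported as a difference between scores.

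**Working it through.** The plan states no figure for this point that could be reproduced. The check is algebraic and uses only the formula and cut-offs in Appendix A.

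**1. Size of the shift.** Let A be the angina index (0, 1 or 2) and ST the deviation in mm.

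- With minutes: DTS = minutes - 5 × ST - 4 × A
- With METs in the time slot: DTS = METs - 5 × ST - 4 × A
- Difference: METs - minutes, because the other two terms cancel.

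**2. Where a class changes.** Set DTS equal to a cut-off and solve for the input. At +5, input = 5 + 5 × ST + 4 × A. At -10, input = -10 + 5 × ST + 4 × A.

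| ST | At +5, A = 0 / 1 / 2 | At -10, A = 0 / 1 / 2 |
|---|---|---|
| 0 mm | 5 / 9 / 13 | -10 / -6 / -2 |
| 1 mm | 10 / 14 / 18 | -5 / -1 / 3 |
| 2 mm | 15 / 19 / 23 | 0 / 4 / 8 |
| 3 mm | 20 / 24 / 28 | 5 / 9 / 13 |

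A patient changes class when minutes and METs lie on opposite sides of the relevant value. Values of zero or below cannot be crossed.

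**3. Examples.** The documents give no relation between METs and minutes, so the gaps here are assumptions.

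| Patient | With minutes | With METs | Assumed gap |
|---|---|---|---|
| 9 min, 1 mm, A = 0 | 9 - 5 = 4, abnormal | 11 - 5 = 6, low risk | +2 |
| 9.5 min, 1 mm, A = 0 | 9.5 - 5 = 4.5, abnormal | 10.5 - 5 = 5.5, low risk | +1 |
| 11 min, 1 mm, A = 0 | 11 - 5 = 6, low risk | 9 - 5 = 4, abnormal | -2 |
| 7 min, 2 mm, A = 2 | 7 - 10 - 8 = -11, high risk | 9 - 10 - 8 = -9, not high risk | +2 |
| 6 min, 1.5 mm, A = 2 | 6 - 7.5 - 8 = -9.5, not high risk | 5 - 7.5 - 8 = -10.5, high risk | -1 |

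Classes change in both directions at both cut-offs.

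**4. Effect on accuracy.** Suppose all patients are classified at +5. A change of class turns a correct call into a wrong one or the reverse, so one patient moves accuracy by 1/n:

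- 100/102 = 0.98 percentage points at the final sample size
- 100/91 = 1.10 percentage points at the sample size before the non-response correction

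Moves in opposite directions can cancel.

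**5. Effect on the AUC.** A gap that is the same for every patient keeps the ranking and leaves the DTS AUC unchanged. A gap that differs between patients could alter the ranking, but nothing in the documents allows this to be sized, and no AUC effect is claimed.

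**The case against.** The strongest reply is that the documents already lean to minutes. The formula names exercise time first, and item 18 of the form records it in minutes. One loose sentence competes with a formula and a matching field, which looks like a drafting slip. METs may be on the form for the Cleveland Clinic Score, whose nomogram is not shown. The sentence carries a 1995 citation that might supply a conversion, and it says only how METs are calculated, not that anyone exercises on a modified protocol.

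Much of this is fair. The lean towards minutes supports the proposed repair, but it does not remove an explicit instruction that says otherwise. A METs field on the form proves nothing by itself. The cited source cannot be consulted here and is missing from the reference list, so the fair statement is that the plan does not print the step. The protocol mismatch is secondary, though the sections still need to agree.

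It is also true that the examples use assumed gaps and patients near a cut-off, that the number reclassified could be zero, and that the 1/n step applies to any misclassification. The condition of classing everyone at +5 is needed because the form allows only low or high and the plan does not place scores between -10 and +5. These points limit the size that can be stated. They do not make the definition consistent.

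**Conclusion.** The point holds: the DTS definition is wrong as written, because the instruction to enter METs does not fit the printed equation and no other section resolves it. Read literally, it shifts each score by METs minus minutes against unadjusted cut-offs. That can change DTS class, accuracy and kappa in either direction.

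The size and sign of the overall effect cannot be determined from the documents. What can be stated is the step of 0.98 to 1.10 percentage points of accuracy per reclassified patient, on the assumptions that METs replace minutes and that all patients are classed at +5. If METs were meant only as a step to an equivalent time, the fault is a missing conversion and the repair is similar. It should be corrected before scoring. Confidence in its practical importance is moderate, because the number of patients affected is unknown.

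**What to change.** Before any patient is scored, reconcile Sampling Procedures, Exercise Treadmill Testing, Appendix A and the Appendix C form so that DTS has one input, one unit and one stated protocol.

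- The input consistent with the printed formula and item 18 is exercise time in minutes. If that is what is meant, take the METs sentence out of the DTS definition.
- If METs were meant as a step towards an equivalent exercise time, print the conversion and apply it before the +5 and -10 cut-offs.
- State on the form which field feeds item 26. Record the protocol for each patient only if a modified protocol was used for some tests.

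The cost is about one sentence in Appendix A. Minutes and METs are both already collected, so any score already entered can be recomputed and no new data are needed.
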